### **4.3 Inclusion Criteria**

Individuals must meet all of the following criteria to be eligible for study participation:

1. Healthy women and men who are  $\geq 18$  and  $\leq 64$  years of age.
2. Able to provide informed consent.
3. Willingness to complete all study visits and comply with all study requirements.
4. Willing to have samples stored for future research.
5. A female is eligible for this study if she meets 1 of the following:
  - Of non-childbearing potential (i.e., women who have had a hysterectomy or tubal ligation or are postmenopausal, as defined by no menses in  $\geq 1$  year).
  - Of childbearing potential but agrees to practice effective contraception or abstinence for 4 weeks prior to enrollment through the completion of the study. Acceptable methods of contraception include a male partner who is sterile and is the sole sexual partner of the female participant or a male partner who uses a condom with spermicide plus 1 or more of the following that is used by the female: 1) implants of levonorgestrel; 2) injectable progestogen; 3) an intrauterine device with a documented failure rate of  $< 1\%$ ; 4) oral contraceptives; and 5) double barrier method including diaphragm.
6. Agrees to not use scented lotions, deodorants, or topical creams on each feeding day.
7. Agrees to not take aspirin or any other NSAID within 7 days of a biopsy.
8. Agrees to not use topical steroid creams or ointments throughout the study without prior permission of Principal Investigator (PI).
9. Vector-specific antibody enzyme-linked immunosorbent assay (ELISA) to one of the three vectors (the one to which the individual is assigned) is  $< 2.5$  standard deviations above the negative control for Cohort A only.

### **4.4 Exclusion Criteria**

Individuals meeting any of the following criteria will be excluded from study participation:

1. Any underlying or current medical condition that, in the opinion of the investigator, would interfere with participation in the study.
2. Any participant that is HIV positive.
3. A clinically significant (as determined by the PI) baseline Grade 1 or greater toxicity by the toxicity table.
4. History of severe allergic reaction (including to mosquito or other insect bites) with generalized urticaria, angioedema, anaphylaxis, or anaphylactoid reaction.
5. Prone to allergic responses and/or significant history of allergies, including seasonal or specific allergies as determined by the PI.
6. Receipt of any investigational drug that is unlicensed within 3 months or 5.5 half-lives (whichever is greater) prior to enrollment.
7. Receipt of any unlicensed vaccine within 6 months prior to enrollment.
8. Self-reported or known history of alcoholism or drug abuse within 6 months prior to enrollment, or positive urine test for drugs of abuse at screening (excluding positive test for tetrahydrocannabinol [THC] or its metabolites if usage is less than 3 times per week).
9. Self-reported or known history of psychiatric or psychological issues that require treatment and are deemed by the PI to be a contraindication to protocol participation.
10. Any use of medications that affect blood clotting within 3 months, history of abnormal blood clotting, or result outside of the normal laboratory range for measurements of prothrombin time (PT), partial thromboplastin time (PTT), or international normalized ratio (INR) that may suggest a problem with blood clotting.
11. History of significant scarring after previous biopsies, lacerations, abrasions, surgeries, or other skin procedures (e.g., cosmetic piercings) that are deemed by the PI to be a contraindication to protocol participation.
12. Pregnant or breastfeeding.

**Co-enrollment Guidelines:** Co-enrollment in other trials is restricted, but may take place after consultation with the study staff and approval from the PI.

#### **4.5 Justification for Exclusion of Special Populations**

**Exclusion of Pregnant Women:** In this study, participants will have multiple exposures to mosquito or sand fly bites. Because pregnant women are known to be immunosuppressed to some degree and the primary objective of the study is to examine immune response to vectors, they will be excluded so as not to compromise the scientific validity of the study.

**Exclusion of Children:** This is a study of the adult immune response to insect bites. Therefore, children will be excluded from the study.

## 5 Study Intervention

### 5.1 Arthropod Feeding

At the Laboratory of Malaria and Vector Research (LMVR), established state of the art insectaries for both mosquitoes and sand flies have been inspected and certified by the USDA as ACL2 (arthropod containment level 2) insectaries. The sand fly colony of *Lutzomyia longipalpis* originates from Brazil and was initially established at the Laboratory of Parasitic Diseases and was brought to LMVR in 2004. The *Aedes aegypti* and *Anopheles gambiae* mosquitoes were first established in 1972 and 1973, respectively. The two colonies were brought to LMVR in 2004. The colonies have been raised in our insectaries since. The insectaries include temperature- and humidity-controlled rooms as well as incubators with temperature, humidity and light cycle controls. We also have experienced technicians that take care of the colonies on a daily basis. For our study, the mosquito pupae collected after emergence will be placed into clean new containers in incubators dedicated to mosquitoes for use in human studies, located in a separate room from the rest of the colony. Both sand flies and mosquitoes used in human studies never come into contact with human blood prior to their use.

Colony-reared, clean female arthropods from each of three species, *Aedes aegypti* mosquitoes, *Anopheles gambiae* mosquitoes, or *Lutzomyia longipalpis* sand flies, will be bred in the insectary at the LMVR at the Twinbrook campus. In Cohort A, participants will undergo one feeding. In Cohort B, participants will undergo 4 feedings by the same vector. Participants will be asked to not use scented lotions, deodorants, or topical creams on each feeding day. Post-feeding, insect bites will be counted. In individuals that lack a robust response to saliva, each bite site will be distinguished by a red pinpoint on the skin, visible to the eye with careful inspection of the skin. Other participants may be more reactive to component of saliva, such as vasodilators, and will exhibit clear redness and/or induration that denotes a clear site of bite.

Each feeding will be conducted as follows:

- i. Assessment of the skin will be documented pre-feeding.
- ii. Depending on the cohort, starved female *Aedes aegypti* mosquitoes, *Anopheles gambiae* mosquitoes, or *Lutzomyia longipalpis* sand flies will be selected from a colony approved for human feeding studies in LMVR, NIAID.
  - a. 5-10 female insects will be aspirated or placed into a secured feeding device prior to feeding and brought to the CC from the LMVR Insectary.
- iii. The feeding site will be wiped clean with mild unscented soap and water and the device will be placed on the participant's arm for up to 20 minutes. The insects will feed through a disposable mesh on the bottom of the feeding device. This device permits the evaluation of feeding on

the human participant at the end of exposure, where the abdomen of blood fed mosquitoes or sand flies will be distended and bright red, and clearly visible through the mesh.

- a. In the unlikely event of no feeding or poor feeding (only 0-2 insects fed or probed as noted by trained staff), the participant may undergo a repeat feed with 5-10 fresh insects once.
  - b. If a repeat feed is required, the post-feeding biopsies and blood draws will be done based on the timing of the repeat feed.
  - c. Post-feeding times will be calculated from the time the feeding device is removed.
- iv. Post-feeding, redness, swelling and number of visible bites will be assessed and documented immediately (+15 minutes) and 30 minutes (+15 minutes) after the feeding device is removed. This may also include taking photographs of the bites.
  - v. Once the mosquitoes or sand flies have fed, they will be brought back to the lab for evaluation and then disposal.

After each feeding, participants may be offered standard treatment as needed to control reactions to vector bites. These treatments may include cold compresses, topical or oral antihistamines, or topical steroids. On days when biopsies will be performed, necessary treatment to control the reaction to the vector bite will be offered after the biopsy is completed. Any necessary treatment to control bleeding, discomfort, or reduce scarring from the biopsy will also be offered.

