### **6.3.1 Vector feeding and biopsy (Days 0, 14, 28, and 42, ±7 days)**

All Cohort B participants will undergo feeding procedures on Days 0, 14 (±7 days), 28 (±7 days), and 42 (±7 days) for a total of 4 feedings. Feedings will be approximately 2 weeks apart with a minimum of 7 days in between feedings. These visits will occur in the SCSU, or other appropriate unit, and the following procedures will be performed:

- Review of medical/medication history.
- Review of inclusion/exclusion criteria.
- Documentation of usual responses to mosquito bites as none (0), mild (1), moderate (2), or severe (3). (only performed on Day 0).
- Clinician exam/assessment.
- Vital signs.
- Urine pregnancy test (for women of childbearing potential; confirmed negative before feeding).
- Blood draw for research labs (section 7.2, Appendix A).

After these procedures, participants will undergo feeding with the assigned vector. Feeding and monitoring will be conducted as described in section 5.1.

After each feeding on Day 0, 14, and 28, participants will be monitored for a minimum of 1 hour post feeding and the following procedures will be performed:

- Any clinical tests that are medically indicated or appropriate to ensure the safety of the individual participant as deemed by the PI.
- Participants will be asked to not apply any topical steroid treatments. Other topical treatments, such as antihistamines, may be applied as needed.

After the final feeding on Day 42, the following procedures will be performed:

- 2 skin punch biopsy collections as follows:
  - 1 biopsy from bitten skin collected no earlier than 3.5 hours and no later than 4.5 hours after the vector feeding is completed.
  - 1 biopsy from unbitten skin on the opposite arm collected no earlier than 30 minutes and no later than 6 hours after the vector feeding is completed.
- Any other clinical tests that are medically indicated or appropriate to ensure the safety of the individual participant as deemed by the PI.
- Participants will be asked to not apply any topical treatments after the fourth and final feeding. Other topical treatments may be applied after the Day 44 biopsy is completed.

Following these study procedures, participants will be allowed to leave as long as there are no safety concerns. They will be provided with medications if needed before they leave, and they will be asked to notify the study team if they have any reactions or side effects.

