**8 Potential Risks and Benefits****8.1 Potential Risks****8.1.1 Risks of vector feeding**

Vector feeding may result in itchiness, pain, swelling, and redness at the site of bites. These reactions resolve after a short period of time and pose little risk to the participant. Applying cold packs and administering over-the-counter pain medications or antihistamines (topical or oral) if necessary can generally treat these reactions. Vector feeding or scratching after vector feeding may result in scarring such as hyperpigmentation. In rare cases a more severe irritation could occur, such as anaphylactic reaction or secondary infection at the site of the bite. Signs of infection include pain, redness, swelling, and drainage at the site. Oral antibiotics or anti-inflammatory medications can be administered if necessary.

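### Cohort B: sections 5.1 and 6.3.1 disagree on topical bite treatment between the Day 42 feeding and the Day 44 biopsy, so the 48-hour primary sample may come from treated skin

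*Combined protocol and SAP*

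**What the plan says.** Section 5.1 covers every feeding in both cohorts. It states: "After each feeding, participants may be offered standard treatment as needed to control reactions to vector bites". It then gives the range: "These treatments may include cold compresses, topical or oral antihistamines, or topical steroids". For biopsy days it adds: "On days when biopsies will be performed, necessary treatment to control the reaction to the vector bite will be offered after the biopsy is completed".

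Section 6.3.1 sets separate rules for Cohort B. After the feedings on Days 0, 14 and 28: "Participants will be asked to not apply any topical steroid treatments. Other topical treatments, such as antihistamines, may be applied as needed". After the Day 42 feeding: "Participants will be asked to not apply any topical treatments after the fourth and final feeding". That restriction ends when the Day 44 biopsy has been taken. The same section has staff supply medication, where needed, as participants go home on Day 42, without limiting type or route.

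Two inclusion criteria in section 4.3 bear on this. Item 6 rules out topical creams on feeding days. Item 8 reads "Agrees to not use topical steroid creams or ointments throughout the study without prior permission", the permission being the principal investigator's.

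The late bitten-skin biopsy is taken at least 40 hours after the fourth feeding (section 6.3.2). It supplies the 48-hour time point of primary endpoints 2a and 2b, with eight participants per vector for immunohistochemistry and seven for transcriptomics (section 3.2.1). Section 14.2 compares bitten with unbitten skin within participants and says nothing about bite treatment used before a biopsy.

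**The concern.** Two biopsies are taken on Day 42, one of them from bitten skin, and the second bitten-skin sample follows about two days later. A rule that releases treatment after the biopsy on a biopsy day therefore releases it before the last primary sample. Section 6.3.1 appears written to prevent that, but nothing says it overrides 5.1.

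The outcome is the local immune response in bitten skin, and the treatments named in 5.1 are given to control the reaction to the bite. Because use is as needed, it would tend to follow the strength of the reaction, so treated samples would not be a random subset. With seven or eight pairs per vector and assay, a few treated samples could matter, and the plan has no rule for identifying or handling them.

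**Working it through.** **1. The two sections side by side, Cohort B, from the end of the Day 42 biopsies to the Day 44 biopsy.**

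| Agent | Section 5.1 | Section 6.3.1 | Compatible? |
|---|---|---|---|
| Topical antihistamine | may be offered | participant asked not to apply | No |
| Topical steroid | may be offered | participant asked not to apply | No |
| Oral antihistamine | may be offered | not addressed; medication may be supplied on leaving | No conflict, but a gap |

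**2. Length of the window.** Inputs: Day 42 bitten-skin biopsy at 3.5 to 4.5 h (6.3.1); late biopsy at 40 h or more, visit on Day 44 with up to 3 days' allowance (6.3.2).
- Shortest: 40 − 4.5 = 35.5 h.
- Nominal: 48 − 4 = 44 h.
- Longest, taking Day 47 as (47 − 42) × 24 = 120 h after feeding: 120 − 3.5 = 116.5 h.

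**3. Samples exposed to the conflict.** 3 vectors × 15 = 45 late biopsies: 3 × 8 = 24 for immunohistochemistry and 3 × 7 = 21 for transcriptomics.

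**4. Does pairing protect the contrast?** No. The control comes from the opposite arm and is taken between 30 minutes and 6 hours after the Day 42 feeding. A topical agent on the bite does not treat the control site. Anything taken after the Day 42 procedures, oral agents included, comes too late to affect the control. Any effect therefore falls on the bitten side only.

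**5. Size.** The plan has no figure to reproduce. As an illustration only, let q be the share of participants treated and f the share of the response that treatment removes, both assumed. If treated participants have an average response, the mean bitten-minus-unbitten difference is multiplied by 1 − q × f.

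| q (assumed) | Multiplier, f = 0.25 | Multiplier, f = 1 | Chance of at least one treated among 8, 1 − (1 − q)^8 | Among 7, 1 − (1 − q)^7 |
|---|---|---|---|---|
| 0.10 | 0.975 | 0.90 | 57% | 52% |
| 0.25 | 0.94 | 0.75 | 90% | 87% |
| 0.50 | 0.875 | 0.50 | 99.6% | 99% |

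If the strongest reactors are the ones treated, the loss for a given q and f is larger than shown. The range runs from trivial to a halving and rests wholly on the assumed inputs.

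**6. The other places.**
- *Feedings 1 to 3.* Section 5.1 lists topical steroids after each feeding and 6.3.1 asks participants not to apply them. The mismatch is real, but no biopsy is taken at those visits.
- *Inclusion item 6.* It rules out topical creams on feeding days, while 5.1, and 6.3.1 for feedings 1 to 3, allow topical treatment after feeding. The item does not say whether it applies only before the feed.
- *Cohort A.* Two bitten-skin biopsies are taken on Day 0, at 30 to 90 minutes and 3.5 to 4.5 h, so 3.5 − 1.5 = 2.0 h to 4.5 − 0.5 = 4.0 h apart. Section 5.1 refers to a single biopsy without saying which. Section 6.2.1 places medication to take home after the day's procedures, which include all three biopsies. This is ambiguity; nothing contradicts 5.1.

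**The case against.** The strongest defence is that 6.3.1 is the specific rule for this visit and 5.1 is general and permissive. Staff working from the Cohort B visit section would keep topical agents off the bite until Day 44, and Day 44 already includes a medication-history review. The study also describes itself as highly exploratory. This lowers the likely frequency of the problem. It does not remove it: no text gives 6.3.1 precedence, oral agents stay open under either section, and no passage asks for the agent and time relative to the biopsy.

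A reader might infer more than the documents support:
- *That the Cohort A 4-hour biopsy faces the same contradiction.* It would need 5.1 to be read as meaning the first of the bitten-skin biopsies, against the order of events in 6.2.1.
- *That section 8.1.1 conflicts with the NSAID restriction in inclusion item 7.* The sentence is "Oral antibiotics or anti-inflammatory medications can be administered if necessary". It follows text on rare severe irritation and infection and names no NSAID.
- *That inclusion item 8 forbids what 5.1 offers.* Item 8 has a permission exception, into which treatment offered by the study team could fit.
- *That the bias has a known size, or certainly runs toward no adaptive response.* The documents say nothing about how these agents alter tissue markers or gene expression. Attenuation is plausible but not established.

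The Cohort B 4-hour bitten-skin biopsy is also less exposed: on the natural reading of 5.1, and under 6.3.1, topical bite treatment does not come before it.

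**Conclusion.** The point holds for Cohort B between the Day 42 feeding and the Day 44 biopsy. The two sections give opposite instructions on topical treatment, and silence on oral antihistamines leaves a further gap. The consequence is confined to the 48-hour contrasts of primary endpoints 2a and 2b, where the bitten side could be treated and the control not. Whether any sample is affected depends on which section staff follow and how many participants want treatment, neither of which the documents settle. No figure for the bias can be defended. The steroid mismatch after feedings 1 to 3 is lesser, and the Cohort A wording only needs clarifying. It should be corrected because a treated biopsy cannot be replaced without another feeding, and the correction is cheap.

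**What to change.** Reconcile sections 5.1 and 6.3.1, and align them with inclusion items 6 and 8, so that one statement governs each feeding. It should say whether oral agents are covered and identify which biopsy is meant in each cohort. Which clinical rule applies is for the protocol team.

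Record the agent, route and time of any bite treatment used before a biopsy. For Cohort B this can be added to the existing Day 44 medication review. In Cohort A the only scheduled medication review is listed before the feeding (section 6.2.1), so the entry has to be made during the Day 0 procedures.

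In section 14.2, pre-specify that the 48-hour contrasts are reported with all participants and again without those treated before that biopsy. Label the second a sensitivity analysis and state its limit: treatment is decided after feeding, so excluding treated participants may remove the strongest reactors and leave even fewer than seven or eight pairs. Neither result should be read as the unbiased one.

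The cost is a wording amendment, one case report form field and one repeat of an analysis already planned.

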## **6 Study Schedule**

This study will take place at the NIH CC. All aspects of the protocol will be carried out in accordance with NIH guidelines, and International Council on Harmonisation (ICH) Good Clinical Practice (GCP) involving human participant research. The study schedule is described below and in [Appendix A: Schedule of Procedures/Evaluations](#).

### **6.1 Enrollment**

At the time of enrollment, participants will be assigned to one of two cohorts and one of three vector groups based on their history of exposure and vector-specific ELISA results performed during screening (for Cohort A only, see [Section 4.3](#)). Vector assignment will also consider participant availability, since not all vectors may be available for feeding on the same feeding day. Participants may be assigned to any of the vectors or groups until a group is full. At that point, participants will only be assigned to vectors and groups that have not been completely enrolled. If a participant is only eligible for a vector or group that is already completely enrolled, they will not continue with consent and enrollment.

The research team will thoroughly discuss the informed consent form with each eligible individual and obtain consent prior to performing any study procedures. This process may take place within 90 days of or on Day 0 before any research procedures are performed.

## **6.2 Cohort A**

Cohort A participants will undergo 1 vector feeding and 3 biopsy procedures, all on Day 0.

### **6.2.1 Vector feeding and biopsy (Day 0)**

The vector feeding will take place in the NIH CC Special Clinical Studies Unit (SCSU) or other appropriate unit. The following procedures will be performed:

- Review of medical/medication history.
- Review of inclusion/exclusion criteria.
- Documentation of usual responses to mosquito or other insect bites as none (0), mild (1), moderate (2), or severe (3).
- Clinician exam/assessment.
- Vital signs.
- Urine pregnancy test (for women of childbearing potential; confirmed negative before feeding).
- Blood draw for research labs (section 7.2, Appendix A).

After these procedures, participants will undergo feeding with the assigned vector. Feeding and monitoring will be conducted as described in section 5.1.

After the feeding, participants will undergo the following procedures:

- 3 skin punch biopsy collections as follows:
  - 1 biopsy from bitten skin collected no earlier than 30 minutes and no later than 90 minutes after the vector feeding is completed.
  - 1 biopsy from bitten skin collected no earlier than 3.5 hours and no later than 4.5 hours after the vector feeding is completed.
  - 1 biopsy from unbitten skin on the opposite arm collected no earlier than 30 minutes and no later than 6 hours after the vector feeding is completed.
  - Biopsies will be placed immediately and no later than one minute after excision into pre-labeled Eppendorf tubes containing either a fixative (10% buffered formalin) or RNAlater for immunohistochemical or transcriptomic analyses, respectively.
- Any other clinical tests that are medically indicated or appropriate to ensure the safety of the individual participant as determined by the PI.

Following these study procedures, participants will be allowed to leave as long as there are no safety concerns. They will be provided with medications if needed before they leave, and they will be asked to notify the study team if they have any reactions or side effects.

